# 1 Synopsis

Protocol Number:	ORFM Pilot 2			
Title:	A Pilot Safety and Pharmacokinetic Study of MB-102 versus Iohexol and the Use of the Non-invasive Optical Renal Function Monitor (ORFM) device, in Subjects with Normal and Impaired Renal Function and a Range of Skin Color Types			
Investigational	MB-102			
Product:	ORFM Prototypes QuantumLeap, Radiance and Brilliance			
Since the initiation of this protocol, the name of the investigational device changed to the Transdermal GFR Measurement System (TGFR) which con 102, the system monitor, and the prototype sensors QuantumLeap, Radiana Brilliance. Supporting documentation may refer to ORFM or TGFR. Both the same investigational device.				
Number of Study Sites:	This study will take place at up to 4 investigational sites in the US.			
Phase:	Pilot 2			
Objectives: Study Design:	
 
To evaluate the safety and tolerability of single dose and multiple doses of MB-102 in subjects with normal and impaired kidney function
 
To determine plasma pharmacokinetics of MB-102 compared to the pharmacokinetics of iohexol in subjects with normal and impaired renal function
 
To show that the MB-102 transdermal fluorescence measured GFR using the ORFM Brilliance device aligns with the measured MB-102 plasma GFR (Group 3)
 
To evaluate the safety and effectiveness of the ORFM investigational medical device prototypes QuantumLeap, Radiance and Brilliance for the non-invasive transdermal fluorescent detection of MB-102 in subjects with a range of skin color types
 
To determine the optimum dose of MB-102 for non-invasive measurement
 
			
Name have of Two stad				
Number of Treated Subjects:	Up to 261 subjects are intended to be enrolled across 3 Groups stratified by cohorts:			
	
 
Group 1: Approximately 60 subjects will be enrolled: Cohort 1: 30 subjects with normal to CKD Stage 2 renal function; and Cohort 2: 30 subjects with impaired renal function [CKD stage 3 – 4]). Fluorescence will be measured by the QuantumLeap ORFM Device.
 
Group 2: Up to 60 subjects will be enrolled: Cohort 3: 20 subjects with normal to CKD Stage 2 renal function, Cohort 4: 40 subjects with impaired renal function [CKD stage 3-5]. Fluorescence will be measured by the Radiance ORFM Device.
 
			
	Approximately 10 subjects from Cohort 4 will undergo extended PK collection (out to 48 hours).			
	Group 1 and Group 2 have been Completed			

**Group 3:** Up to 141 subjects will be enrolled:

- Cohort 5: 8 subjects with normal to CKD stage 2 renal function,
- **Cohort 6**: 8 subjects with impaired renal function [CKD stage 3-5]. Fluorescence will be measured by the Brilliance ORFM Device and algorithm optimization will be performed.

#### **Sensor Optimization Group (SOG)**

In order to further optimize the sensor device, a Sensor Optimization Group (SOG) will be enrolled and consist of 18 healthy subjects with normal to CKD stage 2 renal function. An additional group of 9 healthy subjects may be enrolled into the SOG. Therefore, this cohort of subjects may range from a minimum of 9 subjects up to 27 subjects. SOG subjects will be followed for 12 hours.

#### **Sensor Verification Group (SeVG)**

A Sensor Verification Group (SeVG) will consist of up to 50 subjects to validate the Brilliance sensor. Sites will enroll subjects with normal renal function to Stage 5 CKD. Subjects with normal to stage 2 CKD will be considered the "SeVG-1" group and subject to specific eligibility. Subjects who have impaired renal function (CKD Stage 3-5) will be considered the "SeVG-2" group and subject to specific eligibility requirements.

A subset of subjects (up to 20) who weigh greater than 110 lbs (50 kg) will receive a fixed dose of 7 mL (130 mg).

A study interim analysis will be performed after completion of the SeVG cohort of all previously collected subject data (Groups 1, 2 and 3 through the SevG enrollment). This analysis will be performed to summarize clinical data in support of pivotal trial regulatory discussions. It is not the intention to stop the study early or revamp sample size for the remaining cohorts.

#### Cohorts 7 and 8

An additional 48 subjects may be enrolled to test the optimized algorithm and final device design:

**Cohort 7**: up to 24 subjects with normal to CKD stage 2 renal function. A subset of Cohort 7 subjects will have 2 doses of MB-102 and will be followed for 24 hours. Single dosed cohort 7 subjects will be followed for 12 hours.

Sites enrolling subjects into Cohort 7 (multiple dose group only for Protocol Version 11.0, 12.0 and 13.0) should strive to recruit subjects with a baseline  $eGFR \geq 90$  ml/min/1.73 $m^2$  if feasible. The intent to enroll more normal subjects is to ensure clearance of MB-102 prior to the second dose in order to establish redose timelines for future subjects. In addition, subjects enrolled into the subsets of cohort 7 and 8 (Protocol Version 12.0) should strive to enroll subjects at the extremes of the Fitzpatrick Skin Scale (I and II and V and VI). Finally, subjects enrolled into Cohort 7A and 7B will an eGFR between 90 and 120 ml/min/1.73 $m^2$ . In addition, subjects in Cohort 7B will have a 24 hour period between doses (for a total post dose follow-up period of 36 + hours).

**Cohort 8**: up to 24 subjects with impaired renal function [CKD stage 3-5] will be followed for 48 hours.

Cohorts 7 and 8 will each enroll a set of subjects first to test the algorithm and

	then may be repeated if additional testing is determined to be required.
	A subset of subjects in Cohort 7 and 8 (Cohorts 7A, 8A and 8B) will have a second sensor type placed on the pectoralis or sternum. This sensor (the 2-Part Brilliance Sensor) is being tested to evaluate a removable adhesive ring that would allow future re-use of the sensor portion.
Treatment:	Eligible subjects will receive a single dose of MB-102 followed by a single dose of iohexol (Groups 1 and 2). Group 3, Cohorts 5, 6, SOG, SeVG-1, SeVG-2 and Cohort 8 will only receive a single dose of MB-102 and will not receive iohexol. A subset of subjects in Group 3, Cohort 7 will receive 2 doses of MB-102. Blood draws will be taken at pre-defined timepoints and the Optical Renal Function Monitor (ORFM) fluorescent measurements will be collected over an 8 - 12 hour period or up to 24-48 hours in certain cohorts.
	Group 1, Cohort 1 subjects may receive a range of doses of MB-102. Assessments of coefficient of variation will determine dose optimization. Remaining Group 1 subjects and Group 2 subjects will receive the optimized dose.
	Group 3 subjects (cohorts 5, 6, SOG and over half the subjects in the SeVG cohort will receive a single dose of 4 µmol/kg. A subset of the SeVG cohort (approximately 20 subjects who weigh greater than 110 lbs (50 kg) will receive a fixed dose of 7 mL (130 mg) MB-102.
	Cohorts 7 and 8 (regardless of weight) will all receive a fixed dose of 130 mg (7 mL).
	A subset of Group 3 subjects in Cohort 7 will receive 2 doses of MB-102 (fixed dose of 7 mL (130 mg). The 2 nd dose will be administered 12 hours after the first dose. For Cohort 7B, subjects will receive their 2 nd dose 24 hours after the first dose.
	Sensor placement in all subjects from Groups 1 and 2 will be in two different locations. All Group 1 and 2 subjects will have a single sensor placed on the sternum. A second location will be assigned to determine additional sites for fluorescent measurements. Group 3 subjects may have 2-3 different sensors located on different parts of the body. At least one sensor will be on the sternum or pectoralis major.  • Group 1 subjects will have fluorescent measurements performed by the
	
 
Prototype QuantumLeap device.
 
Group 2 subjects will have fluorescent measurements performed by the Prototype Radiance device.
 

	Group 3 subjects will have fluorescent measurements performed by the Prototype Brilliance device.
	
 
A subset of subjects in Group 3 will also have a 2-part Brilliance sensor placed (cohort 7A, 7B, 8A and 8B)
 

Study Duration per Subject:	Screening period: up to 40 days prior to dosing; dosing day, and a follow-up visit within 7+/-3 days of dosing.
Study Population:	Main Criteria for Inclusion (Group 1 and Group 2):
	• Age ≥ 22 years – male or female

- Eligible female non-pregnant subjects who are either not of childbearing potential or willing to use adequate contraception during the trial
- o Males must be willing to practice abstinence or utilize adequate contraception from dosing day to at least 7 days post dose
- Subjects willing to comply with study requirements
- Subjects who have signed an informed consent form
- Normal or non-clinically significant screening and baseline 12 lead ECG in the opinion of the PI
- Adequate venous access sufficient to allow blood sampling per protocol requirements

#### **Main Criteria for Inclusion (Group 3)**

- Age  $\geq$  18 years male or female
  - Eligible female non-pregnant subjects who are either not of childbearing potential or willing to use adequate contraception during the trial
  - o Males must be willing to practice abstinence or utilize adequate contraception from dosing day to at least 7 days post dose
- Subjects willing to comply with study requirements
- Subjects who have signed an informed consent form
- Normal or non-clinically significant screening and baseline 12 lead ECG in the opinion of the PI
- Adequate venous access sufficient to allow blood sampling per protocol requirements

# Group 1 Cohort 1; Group 2 Cohort 3; and Group 3 Cohort 5, SOG, SeVG-1 Cohort and Cohort 7

- Are healthy as determined by medical history, with no clinically significant findings on screening and baseline physical exams, vital signs and clinical laboratory panels or conditions that could adversely impact the subject's participation or safety, conduct of the study or interfere with study assessments
- Have eGFR (CKD-EPI equation) of ≥60 ml/min/1.73m^2 (normal to Stage 2 CKD) at the time of screening

Approximately half of the patients enrolled in each cohort to have Fitzpatrick Scale Type I, II or III skin color type.

Approximately half of the patients enrolled in each cohort to have Fitzpatrick Type IV, V or VI skin color type.

#### Group 1 Cohort 2

- Possess stable renal function in the opinion of the PI
- Have eGFR (CKD-EPI equation) of 15 59 mL/min/1.73m^2 at the time of screening
- Stable use of immunosuppressant medications (when applicable)
- ~15 subjects per cohort to have Fitzpatrick Type I, II or III skin color type
- ~15 subjects per cohort to have Fitzpatrick Type IV, V or VI skin color type

#### Group 2 Cohort 4, and Group 3 Cohorts 6, SeVG-2, and 8

- Possess stable renal function as defined as the most recent historical (within 3 months) eGFR and screening eGFR differing by ≤20%.
- Have eGFR (CKD-EPI equation) of <59 mL/min/1.73m^2 based on a historical value collected within 3 months or from the screening serum creatinine
- Stable use of immunosuppressant medications (when applicable) defined as no changes in the last 30 days or expected through the follow up visits, and a prednisone dose of <20 mg/day (or another steroid's equivalent dose).

Approximately half of the subjects in each cohort to have Fitzpatrick Type I, II or III skin color type

Approximately half of the subjects in each cohort enrolled to have Fitzpatrick Type IV, V or VI skin color type

#### Main Criteria for Exclusion (Group 1)

- Women who are pregnant, lactating or planning to become pregnant during the study, or women who are of childbearing potential unwilling to use a barrier method of birth control
- Intolerant to venipuncture
- Recent donation or loss of blood or plasma: 100 mL to 499 mL within 30 days prior to the initial dose of the study medication; or more than 499 mL within 56 days prior to the initial dose of study medication
- Participation in another interventional trial within 30 days of screening or concurrently enrolled in any other medical research study which could impact the results of the study
- History of drug or alcohol abuse within the past year
- History of allergy or hypersensitivity to MB-102 or iohexol, or other related (iodinated contrast media) products, or any of the inactive ingredients
- History of skin sensitivity to adhesives (e.g. Band-Aids, surgical tape)
- Any food allergy, intolerance, restriction or special diet that, in the opinion of the Principal Investigator, could contraindicate the subject's participation in this study
- Subjects who have allergies to 2 or more classes of drugs. (*Intolerance to a drug is not considered a drug allergy*)
- Stable use (no changes within 30 days) of prescription or OTC medications
- NSAID use within 2 days of dosing day
- History of coagulation disorders or bleeding disorders that in the judgement of the investigator places the subject at undue risks for study related procedures
- Are homozygous for sickle cell disease
- Have a known thyroid disorder
- Have pheochromocytoma
- Currently on Coumadin (warfarin) who have an INR>4 at Screening
- Current history of AIDS or HIV
- Hepatitis B antigen positive, or C antibody positive
- Site personnel immediately associated with the study or their immediate

#### family members

- Any characteristics which, in the opinion of the investigator, makes the subject a poor candidate for participation in the clinical trial
- Prior enrollment and dosing in this Pilot 2 study
- Significant scaring, tattoos or alterations in pigmentation on the sternum that would alter sensor readings versus other areas of the skin

#### Additional Exclusion: Group 1 Cohort 1

• History of significant cardiovascular disease, heart failure, myocardial infarction in the past 3 months, pulmonary, hematologic, endocrine, hepatobiliary, nephrologic, immunologic, dermatologic, neurologic (including any history of stroke and/or seizure disorder), psychological, musculoskeletal disease, diagnosis of cancer with the past 2 years or deemed clinically significant or unstable by the Principal Investigator; Note: history of gallstones or kidney stones are not excluded so long as the condition is not acute within 30 days of dosing.

# Additional Exclusion: Group 1 Cohort 2

- Stage 5 CKD at the time of screening
- Recent (within 3 months) significant medical condition or surgical procedure including myocardial infarction, laparoscopic procedures, or other medical inventions
- Doses of prednisone greater than 10 mg/day within the last 90 days

#### Main Criteria for Exclusion: (Group 2)

- Women who are pregnant, lactating or planning to become pregnant during the study, or women who are of childbearing potential unwilling to use a barrier method of birth control
  - o Males must be willing to practice abstinence or utilize adequate contraception from dosing day to at least 7 days post dose
- Unable to have venous access placed in both arms
- Recent donation or loss of blood or plasma: 100 mL to 499 mL within 30 days prior to the initial dose of the study medication; or more than 499 mL within 56 days prior to the initial dose of study medication
- Participation in another interventional trial within 30 days of dosing or concurrently enrolled in any other medical research study which could impact the results of the study
- History of drug or alcohol abuse within the past year
- History of skin sensitivity to adhesives (e.g. Band-Aids, surgical tape)
- History of severe allergic hypersensitivity reactions (unacceptable adverse events) or anaphylactoid reaction to any allergen including drugs, MB-102 and iohexol or other related (iodinated contrast media) products (intolerance to a drug is not considered a drug allergy).
- NSAID use within 2 days of dosing day
- History of coagulation disorders or bleeding disorders that in the judgement of the investigator places the subject at undue risks for study related procedures
- Are homozygous for sickle cell disease
- Have hyperthyroidism or current thyroid cancer
- Have pheochromocytoma

- Currently on Coumadin (warfarin) who have an INR>4 at Screening
- Current history of AIDS or HIV
- Current evidence of an active Hepatitis B or C infection. *If the subject is Hepatitis C antibody positive, but the hepatitis C RNA is below the level of detection, they are considered immune and may be eligible for enrollment.*
- Site personnel immediately associated with the study or their immediate family members
- Any characteristics which, in the opinion of the investigator, makes the subject a poor candidate for participation in the clinical trial
- Prior exposure to MB-102
- Significant scaring, tattoos or alterations in pigmentation on the sternum that would alter sensor readings versus other areas of the skin

#### Main Criteria for Exclusion: (Group 3)

- Women who are pregnant, lactating or planning to become pregnant during the study, or women who are of childbearing potential unwilling to use a barrier method of birth control
  - Males must be unwilling to practice abstinence or utilize adequate contraception from dosing day to at least 7 days post dose
- Unable to have venous access
- Recent donation or loss of blood or plasma: 100 mL to 499 mL within 30 days prior to the initial dose of the study medication; or more than 499 mL within 56 days prior to the initial dose of study medication
- Participation in another interventional trial within 30 days of dosing or concurrently enrolled in any other medical research study which could impact the results of the study
- History of drug or alcohol abuse within the past year
- History of skin sensitivity to adhesives (e.g. Band-Aids, surgical tape)
- History of severe allergic hypersensitivity reactions (unacceptable adverse events) or anaphylactoid reaction to any allergen including drugs, or MB-102 (*intolerance to a drug is not considered a drug allergy*).
- NSAID use within 2 days of dosing day
- History of coagulation disorders or bleeding disorders that in the judgement of the investigator places the subject at undue risks for study related procedures
- Currently on Coumadin (warfarin) who have an INR>4 at Screening
- Current history of AIDS or HIV
- Current evidence of an active Hepatitis B or C infection. *If the subject is Hepatitis C antibody positive, but the hepatitis C RNA is below the level of detection, they are considered immune and are be eligible for enrollment.*
- Site personnel immediately associated with the study or their immediate family members
- Any characteristics which, in the opinion of the investigator, makes the subject a poor candidate for participation in the clinical trial
- Significant scaring, tattoos or alterations in pigmentation on the sternum that would alter sensor readings versus other areas of the skin

Additional Exclusion: Group 2 Cohort 3, and Group 3 Cohorts 5, SOG, SeVG-1 and Cohort 7

	History of significant cardiovascular disease, heart failure, myocardial infarction in the past 3 months, or NYHA class III or IV HF
	• Any other serious or uncontrolled medical disorder, active infection, physical exam finding, laboratory finding, or psychiatric condition that in the opinion of the investigator would limit the subjects' ability to complete study requirements or may put the subject at increased risk or compromise interpretability of study results. Note: a history of gallstones or kidney stones are not excluded so long as the condition is not acute within 30 days of dosing.
	Additional Exclusion: Group 2 Cohort, 4 and Group 3 Cohorts 6, SeVG-2, and 8
	
 
Recent (within 3 months) significant medical condition or surgical procedure including myocardial infarction, thoracic laparoscopic procedures, or other significant medical inventions
 
Received >20 mg/day of prednisone or an equivalent dose of glucocorticoid for more than 7 days in the last 90 days prior to dosing day
 

	for an acute or chronic disorder
	Currently receiving dialysis
	Currently anuric
Primary Endpoint:	
 
Determine plasma pharmacokinetics of MB-102 compared to the pharmacokinetics of iohexol in subjects with normal and impaired renal function and a range of skin color types (Groups 1 and 2)
 
To show that the MB-102 transdermal fluorescence measured GFR using the ORFM Brilliance device matches the measured MB-102 plasma GFR (Group
 

Casandawy	3) SATE 14 1 SATE 102
Secondary Endpoints:	• Evaluate the safety and tolerance of MB-102
Endpoints:	• Evaluate the safety of the ORFM devices for the noninvasive transdermal fluorescent detection of MB-102
	• Evaluate the effectiveness of the ORFM devices (QuantumLeap, Radiance and Brilliance) through the comparison of fluorescent measurements versus MB-102 across the three groups of subjects
	Determine the optimum dose of MB-102 for noninvasive measurement
Primary Safety Endpoint:	Adverse events (AEs and serious AEs [SAEs], UADEs)
Statistical Methods and Sample Size	As this is a Pilot Study, no formal calculation of sample size was conducted.
Calculations	Safety will be evaluated as the incidence of AEs and SAEs/UADEs. These will be summarized by cohort and overall.
Time Schedule:	Planned Start of Study: April 2016
i inic schedule.	
	Planned End of Study: Sep 2021

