### 4 Study Objectives

The objectives of this pilot study are:

- To evaluate the safety and tolerability of single dose and multiple doses of MB-102 in subjects with normal and impaired kidney function
- To determine plasma pharmacokinetics of MB-102 compared to the pharmacokinetics of iohexol in subjects with normal and impaired renal function (Groups 1 and 2)
- To show that the MB-102 transdermal fluorescence measured GFR using the ORFM Brilliance device aligns with the measured MB-102 plasma GFR (Group 3)
- To evaluate the safety and effectiveness of the ORFM investigational medical device prototypes QuantumLeap, Radiance and Brilliance for the non-invasive transdermal fluorescent detection of MB-102 on subjects with a range of skin color types
- To determine the optimum dose of MB-102 for non-invasive measurement

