#### **Group 3:** Up to 141 subjects to be enrolled:

- Cohort 5: 8 subjects to have normal to CKD Stage 2 renal function
- Cohort 6: 8 subjects with impaired renal function (CKD stage 3-5)
- Sensor Optimization Group (SOG): 18 subjects with normal to CKD Stage 2 renal function; if optimization still requires additional work; a third and final group of 9 subjects will be enrolled to finalize the device and algorithm design.
- Sensor Validation Group (SeVG): up to 50 subjects will be enrolled who have normal renal function to Stage 5 CKD. A subset of subjects (approximately 20) who weigh greater than 110 lbs (50 kg) will receive a fixed dose of 7 mL (130 mg). Subjects receiving the fixed dose may be normal or renally compromised.

A study interim analysis will be performed after completion of the SeVG cohort of all previously collected subject data (Groups 1, 2 and 3 through the SevG enrollment). This analysis will be performed to summarize clinical data in support of pivotal product development and regulatory submissions. It is not the intention to stop the study early or revamp sample size for the remaining cohorts.

The final algorithm and sensor will be further tested in up to 48 additional subjects:

- Cohort 7: up to 24 subjects to have normal to CKD Stage 2 renal function
  - A subset of cohort 7 subjects will have 2 doses of MB-102; the 2nd dose of MB-102 will be administered 12 hours after the first dose (original Cohort 7, 7A)
  - A subset of subjects (Cohort 7B) will have 2 doses of MB-102; the 2nd dose of MB-102 will be administered 24 hours after the first dose
- Cohort 8: up to 24 subjects with impaired renal function (CKD stage 3-5) and followed for 24-48 hours
- All cohort 7 and 8 subjects will receive the fixed dose of 130 mg (7 mL).

Cohorts 7 and 8 will be divided into the following subsets in order to test additional sensor types in development. These subsets are outlined in **Table 2**.

Cohort	Dosing	Follow-up (Hrs)	Sensors	Enrollment
Subgroups				
Cohort 7	Single or 2 doses	12 - 24 hours	Brilliance (1-2 sensors/subject)	Up to 24
Cohort 7A	Single or 2 doses	12 - 24 hours	Brilliance (1-2 sensors/subject) and Brilliance 2-part sensor	subjects
Cohort 7B	2 doses	36 hours	Brilliance (1-2 sensors/subject) and Brilliance 2-part sensor	
Cohort 8	Single dose	48 hours	Brilliance (1-2 sensors/subject)	Up to 16
Cohort 8A	Single dose	48 hours	Brilliance (1-2 sensors/subject) and Brilliance 2-part sensor	subjects

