#### 5.2.2 Group 3 Dosing

Subjects enrolled in Group 3, Cohorts 5, 6, SOG and part of the SeVG group will receive a dose of 4 µmol/kg of MB-102. No dose optimization work will be conducted.

A subset of SeVG subjects (up to 20 subjects who weigh greater than 110 lbs [50 kg]) and all subjects in cohorts 7 and 8 will receive a fixed dose of 7 mL (130 mg). This dose is equivalent to what a 191 lb subject would receive if dosed at the standard 4 µmol/kg dose level. This dose change is within the safety margin of previously performed non-clinical studies. The purpose of testing a fixed dose level is to determine if such a dose will be adequate across a variety of subject weights and still remain an accurate measurement of tGFR. A fixed dose level would simplify dose preparation when the product goes to market.

A subset of subjects enrolled into Cohort 7 will receive 2 doses of MB-102 (both doses will at the fixed dose level of 7 mL or 130 mg). The 2nd dose of MB-102 will be administered either 12 hours or 24 hours (Cohort 7B) after the first dose.

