## **Treatment-Emergent Adverse Events**

AEs will be coded using the *Medical Dictionary for Regulatory Activities* (MedDRA). The system organ class and preferred term for each AE will be available, along with the verbatim reported term, event start and stop dates/times, seriousness, severity, relationship to treatment/device, action taken, and event outcome. SAEs will also be documented in a case narrative format.

The overall numbers and percentages of subjects who experienced any treatment-emergent AE (TEAE), will be presented. AEs will be presented by system organ class, and preferred term.

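### Adverse events are to be summarised by cohort and overall, which does not separate the two-dose subjects in Cohorts 7 and 7A or the fixed-dose subjects in SeVG

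*Combined protocol and SAP*

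**What the plan says.** - **Layout of the safety summary.** The synopsis (statistical methods) plans the incidence of AEs and SAEs/UADEs and states: "These will be summarized by cohort and overall". Section 9.1.4 says: "The overall numbers and percentages of subjects who experienced any treatment-emergent AE (TEAE), will be presented". It then adds presentation by system organ class and preferred term. Neither place names dose level, number of doses, or onset relative to a second dose.
- **Objective.** The first objective in Section 4 is "To evaluate the safety and tolerability of single dose and multiple doses of MB-102 in subjects with normal and impaired kidney function". The synopsis makes adverse events the primary safety endpoint.
- **Cohort 7.** The synopsis says: "A subset of Cohort 7 subjects will have 2 doses of MB-102 and will be followed for 24 hours". Table 2 in Section 5.1 gives the dosing of both Cohort 7 and Cohort 7A as "Single or 2 doses". For the remaining subset Section 5.1 says: "A subset of subjects (Cohort 7B) will have 2 doses of MB-102", with the doses 24 hours apart.
- **SeVG.** Section 5.2.2 says that Cohorts 5, 6, SOG and "part of the SeVG group will receive a dose of 4 µmol/kg of MB-102". Up to 20 SeVG subjects above 50 kg, and all of Cohorts 7 and 8, receive a fixed 130 mg. Section 5.1 adds that the SeVG fixed-dose subjects may come from either renal-function category.

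**The concern.** Cohorts were built around renal function and device phase, so a cohort row is not a regimen row. A reader who wants the adverse event rate after two doses finds in Cohorts 7 and 7A a percentage that mixes subjects given one injection with subjects given two. The two kinds of subject are also watched on site for different lengths of time: 12 hours after a single dose against 24 hours for two. In SeVG a reader who wants to compare fixed with weight-based dosing finds both in one row. Showing SeVG-1 and SeVG-2 separately does not help, because the fixed dose crosses that split.

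At stake is whether the reported tables answer the first objective. If tolerability did differ with a second dose, or at the higher µmol/kg that the fixed dose gives lighter subjects, the stated layout would average that difference with the single-dose or weight-based experience.

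**Working it through.** **1. The plan's own counts reproduce.** Section 8.1 reports 120 subjects on 4 µmol/kg with iohexol, 70 on 4 µmol/kg alone and 12 on fixed 130 mg: 120 + 70 + 12 = 202. Its adverse event rate is 22/202 = 10.9%, as stated. That one rate already pools regimens: fixed-dose subjects are 12/202 = 5.9% of the denominator and have no rate of their own. Planned enrolment also reproduces: Group 3 is 8 + 8 + 27 + 50 + 48 = 141, and 60 + 60 + 141 = 261.

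**2. Planned maxima by regimen.**

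| Regimen | Source | Maximum |
|---|---|---|
| 4 µmol/kg + iohexol | Groups 1 and 2: 60 + 60 | 120 |
| 4 µmol/kg alone | Cohorts 5, 6, SOG, rest of SeVG: 8 + 8 + 27 + 30 | 73 |
| Fixed 130 mg, one or two doses | SeVG subset, Cohorts 7 and 8: 20 + 48 | 68 |
| Total | | 261 |

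The two-dose subjects lie within the last regimen and number at most 24. Neither their number nor the split among 7, 7A and 7B is stated.

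**3. What a by-cohort table shows.**
- *Fixed dose:* 48/68 = 71% are in cohorts where everyone receives it, and 20/68 = 29% are mixed into SeVG, where they make up 20/50 = 40% of the cohort. To date, assuming that all 12 fixed-dose subjects are in SeVG and that 202 − 120 − 8 − 8 − 18 = 48 SeVG subjects were treated, the share is 12/48 = 25%.
- *Two doses:* if Cohort 7 is tabulated as one row, no two-dose subject is isolated. If subsets have their own rows, only 7B is. The plan does not say which is meant.

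**4. Size of the averaging (illustration only).** Let s be the two-dose share of a mixed row, p2 an assumed two-dose rate, and take the 10.9% above as the one-dose rate. The row shows s × p2 + (1 − s) × 0.109. With p2 = 30%:
- s = 25% gives 15.7%
- s = 50% gives 20.4%
- s = 75% gives 25.2%

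Over p2 from 20% to 40% and s from 25% to 75%, the row ranges from 13.2% to 32.7%. For SeVG with a 40% fixed-dose share and an assumed fixed-dose rate of 30%, it shows 0.4 × 0.30 + 0.6 × 0.109 = 18.5%. The documents give no rate by regimen, so p2 and s are assumptions.

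**5. Spread of delivered dose.** Table 1 equates 200 µmol/kg with 74.4 mg/kg, which is 0.372 mg/µmol. A fixed 130 mg is then 130/(0.372 × 50) = 7.0 µmol/kg at 50 kg and 130/(0.372 × 120) = 2.9 µmol/kg at an assumed 120 kg. At 191 lb (191 × 50/110 = 86.8 kg) it is 4.0 µmol/kg, which agrees with the equivalence in Section 5.2.2.

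**6. What separate cells could show.** With zero events the one-sided 95% upper bound is 1 − 0.05^(1/n): 31% at n = 8, 22% at n = 12, 12% at n = 24. These are descriptive cells.

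**The case against.** The strongest answer is that the cohort layout does more than it first appears to, and much of that answer stands.

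- A reader might infer that fixed-dose tolerability cannot be seen at all. It can: Cohorts 7 and 8 are entirely 130 mg, and Cohort 8 is purely single-dose. The stated purpose of the fixed dose, "The purpose of testing a fixed dose level is to determine if such a dose will be adequate across a variety of subject weights", together with tGFR accuracy, is also not a safety question. The multiple-dose half of the point is therefore the stronger one.
- A reader might infer that two-dose subjects are never separated. Cohort 7B separates some of them, if subsets are tabulated.
- A reader might object that iohexol is confounded with MB-102. Only the overall row pools it. Iohexol is confined to Cohorts 1 to 4, so the cohort rows separate it.
- A reader might infer that the mixing damages the evidence for pivotal discussions. The interim analysis in Section 9.1.5 covers data through SeVG and so precedes Cohorts 7 and 8. Only the SeVG mixing reaches it. The redosing rationale concerns clearance of MB-102 before the second dose, not adverse event rates.
- A reader might add two doses at 50 kg to get 14 µmol/kg. At the roughly 2-hour half-life given for normal kidneys, six half-lives leave (1/2)^6 = 1.6% of the first dose at 12 hours, though more where clearance is slower. The sum is not a concurrent exposure.

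Replacing cohort tables with regimen tables would also bring its own confounding. Two-dose subjects are all normal to CKD stage 2, while Cohort 8 is all CKD stage 3 to 5. Finally, Sections 9.1.4 and 9.1.8 leave some details to a SAP. The combined document has no separate SAP text, so a breakdown there cannot be excluded, although the adverse event layout is not among the items deferred.

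What none of this meets is the remaining gap: the two-dose subjects in 7 and 7A, and the fixed-dose subjects in SeVG, have no table of their own.

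**Conclusion.** The point holds in a limited form. The stated adverse event tables do not match the first objective, because they isolate neither all two-dose subjects nor the fixed-dose subjects in SeVG. By planned maxima that leaves up to 20 of 68 fixed-dose subjects unseparated, and an unstated number, at most 24, of two-dose subjects separated only to the extent that they are in 7B and 7B has its own row. The documents do not support a claim that a dose-related signal exists or has been hidden. The dilution figures are illustrations, and in a pilot with no sample-size calculation even a full split would describe rather than test.

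The counts rest on two readings that the plan should settle:
- Section 13.5 words the fixed-dose allocation so that it can be read as covering only part of Cohort 7, whereas the synopsis and Sections 5.1, 5.2.2 and 6.4 say all of it.
- The headings in Section 5.5.2 cap Cohorts 7 and 8 at 16 each, against 24 each elsewhere. With 16 each, the visible share would be 32/52 = 62%.

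The dose range planned for Cohort 1 adds no mixing, since Section 8.1 reports all 120 subjects of Groups 1 and 2 at 4 µmol/kg.

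**What to change.** Keep the by-cohort tables, and say whether 7A, 7B, 8A and 8B have their own rows. Add to the synopsis and Section 9.1.4 a supplementary safety summary by regimen received:

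1. 4 µmol/kg plus iohexol
2. 4 µmol/kg alone
3. single 130 mg
4. two 130 mg doses 12 hours apart
5. two 130 mg doses 24 hours apart

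Present it within renal-function stratum (normal to CKD stage 2; CKD stage 3 to 5), so that number of doses is not confused with kidney function. For two-dose subjects, split TEAEs by onset before or after the second dose. In the listings, show the delivered µmol/kg beside each event. Reconcile the Section 13.5 wording and the Cohort 7 and 8 sizes with the rest of the protocol.

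The cost is a change to the plan's wording and a few extra tables, some with very small cells that allow description only. No new data are needed: Section 9.1.4 provides for event start and stop dates and times, the Section 6.1 schedules record the time of each administration, and weight is measured.
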